#### DBS 1.3.2. Objective

The primary objective of the cohort substudy is to characterize the overall adherence for each treatment group.

### **DBS 1.3.3.** Implementation

In order to lower the burden on the laboratory analyzing DBS cards, subsets of DBS cards will be sent to the analytic laboratory. This will be done by sending subsets of Week 4 samples first. Week 12 subsets of samples will be sent when Week 4 samples have been analyzed and etc. as subjects complete the study visits. For example, as of February 2018, all subjects had completed their Week 24 visit and we could potentially process Weeks 4, 12 and 24 samples for the randomly selected subjects. The size of the batch will depend on the logistics at the analytic laboratory. Further details are provided in the charter for DBS sample analysis project plan conducted at Colorado Antiviral Pharmacology Laboratory (University of Colorado).

The unblinded statistician supporting the external DMC will execute a SAS program to select, for each batch, the accession numbers in the cohort substudy and will:

- 1) Provide the accession number of the selected DBS cards to Covance (central warehousing lab for DBS cards) for transfer to the analytic lab (University of Colorado). Covance will receive the following information: Investigator ID, Subject ID, Lab Date, Accession Number and Container Number (of sample storage at Covance).
- 2) Provide the treatment code for each accession number to the analytic lab as measuring DBS concentration for F/TAF requires a bigger punch-hole on the DBS card compared to F/TDF. The analytic lab will receive the following information: Investigator ID, Subject ID, Lab Date, Treatment group and Accession Number.

#### DBS 1.3.4. Statistical Analysis

Summary tables, similar to those for the main study, will characterize the Cohort substudy for enrollment by country and investigator, demographics and baseline characteristics, baseline HIV risk characteristics, and subject disposition.

Descriptive statistics (n, mean, standard deviation, median, quartiles, minimum and maximum) for DBS TFV-DP concentration levels will be provided by treatment group and visit.

Median (Q1, Q3) of DBS concentration across visit time (horizontal axis) overlaid by horizontal lines corresponding to adherence thresholds for each treatment group, will be generated by treatment group.

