Appendix Table 10. Estimated Dose and F/TDF PrEP Protection Associated with DBS Concentration

DBS Concentration (fmol/punch)	<llq< th="">LLQ-349	350-699	700-1249	≥1250	</llq<>	LLQ-349	350-699	700-1249	≥1250
Estimate dose (tablets/week)	None	<2	2–3	4–6	7
Follow-up (% of visits)	25%	26%	12%	21%	12%
HIV-1 infections (n)	18	9	1	0	0
Person-years per infection	384	399	179	316	181
HIV-1 incidence (95% CI)	4.70 (2.99–7.76)	2.25 (1.19–4.79)	0.56 (0.00–2.50)	0.00 (0.00–0.61)	0.00 (0.00–1.06)

Source: Uptake of pre exposure prophylaxis, sexual practices, and HIV 1 incidence in men and transgender women who have sex with men: a cohort study {Grant 2014}.

A more recent pharmacokinetic study of TFV-DP in DBS using DOT dosing of F/TDF (at daily dosing of 33%, 67%, or 100%) {Anderson 2018} has also shown consistent results. The modeling of data from this study has shown that the fitted (estimated) median (25 and 75 percentiles) TFV-DP DBS concentrations in men, were 375 (316, 444), 774 (653, 917) and 1389 (1173, 1646) fmol/punch for 2, 4 and 7 doses per week respectively {Anderson 2018}.

Considering that F/TAF delivers a lower dose of tenofovir and that using a 3 mm punch disk to quantify the TFV-DP levels in RBC are approximately 1/8th the values established for F/TDF, two 7 mm punched disks (an increase of 10.89 folds in total sample disk area) are used to quantify TFV-DP DBS concentration for participants who receive F/TAF.

A separate cross-over pharmacokinetic study of TFV-DP in DBS based on DOT dosing of F/TAF (at daily dosing of 33%, 67%, or 100%) is currently ongoing. Available preliminary data from this ongoing study {Yager 2019} (CROI abstract and presentation), and the previous F/TDF DOT study {Anderson 2018}, are used to develop the adherence bands for F/TAF based on DBS concentration. The observed 25th percentile, median and 75 percentiles from these sources are presented in Appendix Table 11.

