Appendix Table 11. Reported Estimates of DBS Concentrations at Different DOT Dose Levels

Daily Dosing in DOT Study Treatment		Q1	Median	Q3
33%	F/TDF (fmol/Punch)	424	518	670
	F/TAF (fmol/Punches) - Abstract	613	663	741
	F/TAF (fmol/Punches) - Presentation	510	663	788
67%	F/TDF (fmol/Punch)	806	946	1174
	F/TAF (fmol/Punches) - Abstract	991	1351	1586
	F/TAF (fmol/Punches) - Presentation	1030	1422	1683
100%	F/TDF (fmol/Punch)	1315	1542	1796
	F/TAF (fmol/Punches) - Abstract	1526	1928	2559
	F/TAF (fmol/Punches) - Presentation	1909	2199	2518

Ref: For F/TDF: {Anderson 2018} and F/TAF: Abstract {Yager 2019} and presentation

As expected (relative to TDF dose in F/TDF and DBS disk size), a shift up in the distribution of reported TFV-DP concentrations for F/TAF, compared to F/TDF, in Appendix Table 11 is observed; ~30% based the Week 12 data (Period 1 of the cross over study) and ~35% based the Weeks 12 and 24 data (Period 1 and 2 of the cross over study) included in the analysis of the abstract and presentation respectively. The cutoffs for F/TAF adherence levels can be estimated by adjusting the established DBS concentration for F/TDF adherence levels associated with HIV protection (or risk of acquiring infection) reported by {Grant 2014}, see Appendix Table 10. The proposed cutoffs, by either using 30% increase based on Period 1 results (free of any potential impact of cross-over design) or assuming dose proportionality and relying on Q1 for the 33% and 67% dosing levels, are presented in Appendix Table 12.

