## DBS 1.4.7. Statistical Analysis

Summary tables, similar to those for the main study, will characterize the cases' and controls' demographics and baseline characteristics, baseline HIV risk characteristics and subject disposition by treatment group.

Graphical and/or tabular descriptive statistics (n, mean, standard deviation, median, quartiles, minimum and maximum) for DBS drug concentration levels for both cases and controls in each treatment group will be provided. Conditional logistic regression model will be used to estimate the odds ratio (and its 95% confidence interval) assessing the association between infection status and the adherence levels based on DBS concentration at HIV diagnosis for cases and controls. The 3 level adherence (Appendix Table 12) will be dichotomized to estimate two odds ratios:

- 1) the odds of HIV infection when adherence is low compared to when adherence is not low
- 2) the odds of HIV infection when adherence is high compared to when adherence is not high

The primary analysis will be within each treatment group and will include DBS drug concentration levels, at the time of infection as the primary predictor. If a control subject has DBS collected at more than one visit within a window, then the record with DBS collection study day closest to the diagnosis study day of the case subject will be selected and if they are equally apart from the diagnosis study day of the case subject (one before and one after) then the one after the study day of the case subject will be selected.

DBS cards at the time of diagnosis may not have been collected for infected subjects or the sample may not meet specifications and be rejected by the analytical laboratory. In general, missing DBS concentration at the time of HIV diagnosis will be imputed by considering:

- 1) the last known TFV-DP concentration (C) prior to diagnosis
- 2) days between the last dose date and HIV diagnosis (HIV Dx date last dose date) where any negative days (last dose is after HIV Dx) are set to 0
- 3) days between the last TFV-DP concentration (C) prior to diagnosis and HIV diagnosis (HIV Dx date last DBS date)
- 4) the decay rate, k, of TFV-DP concentration in RBC calculated based on half-life,  $t_{1/2}$ , of each treatment group, where k  $0.693/t_{1/2}$ .

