TFV-DP has shown the median (range) half-life of 17 (14 to 23) days for F/TDF in previous DOT studies of F/TDF {Anderson 2018} and median (IQR) 20 days (18, 21) for F/TAF (preliminary data from Yager 2019 CROI presentation).

[figure not shown]
A sensitivity analysis will be conducted by setting the adherence level to "Low", for subjects suspected to have acquired HIV prior to first dose date of study drug. These are defined as subjects for whom HIV infection prior to first dose date of study drug cannot be excluded as the subjects did not have a Covance HIV antibody or HIV-1 RNA test analyzed between first dose date (inclusive) and prior to the date of diagnosis of HIV infection).

Stratified Wilcoxon test (stratified based on matching criteria) will test the difference between distribution of DBS concentrations (continuous measure) observed in cases and controls. The two-sided p-value from the stratified Wilcoxon test will be reported.

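### The fixed DBS adherence cut-offs ignore incomplete TFV-DP accumulation in the Week 4 window (Days 1 to 56), so about 4 to 5 doses a week reads Medium instead of High

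*SAP*

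**What the plan says.** SAP Appendix 9, DBS 1.2, treats the TFV-DP concentration in dried blood spots as a measure of cumulative exposure. Appendix Table 12 turns it into Low, Medium and High (under 2, 2 to 3, and 4 or more tablets a week). There is one set of cut-offs per arm and none specific to a visit. The F/TAF set is the F/TDF set raised by a shift of about "30% based the Week 12 data (Period 1 of the cross over study").

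The cut-offs are used in two places. In the cohort substudy (DBS 1.3.4), the plot of median and quartiles by visit is "overlaid by horizontal lines corresponding to adherence thresholds for each treatment group". Week 4 cards are assayed first (DBS 1.3.3), so Week 4 is on that plot. In the case-control substudy (DBS 1.4.7), conditional logistic regression gives odds ratios "assessing the association between infection status and the adherence levels based on DBS concentration at HIV diagnosis for cases and controls", using the Appendix Table 12 levels. The Week 4 window for matching runs from Day 1 to Day 56 (Appendix Table 13).

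DBS 1.4.7 also gives the kinetics: "TFV-DP has shown the median (range) half-life of 17 (14 to 23) days for F/TDF", and "median (IQR) 20 days (18, 21) for F/TAF", the latter from preliminary data. First-order decay is used there only to impute a missing concentration at diagnosis. Neither accumulation nor early sampling is addressed for the bands.

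**The concern.** A marker with a half-life of 17 to 20 days takes well over four weeks to build up. A cut-off set on established dosing will therefore under-call adherence in someone who started study drug recently.

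Two readings are affected. On the cohort plot, apparent adherence would rise from Week 4 to Week 12 partly because drug is accumulating. In the case-control analysis, banding depends on the sampling day as well as on pill-taking, and matching is on arm and visit window, not on day. A case sampled early in the window can then score below equally adherent controls, which looks like a link between low adherence and infection. That link is the substudy's primary question (DBS 1.4.2). Power is illustrated with 10 cases per arm (DBS 1.5), so one misbanded case would be a tenth of an arm's cases.

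**Working it through.** **The plan's own figure.** 350 × 1.30 = 455 and 700 × 1.30 = 910, which round to the stated 450 and 900.

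**Inputs.** Half-lives h are 17 days (F/TDF, range 14 to 23) and 20 days (F/TAF, IQR 18 to 21), from DBS 1.4.7. Directly observed dosing quartiles come from Appendix Table 11. Fitted F/TDF values in men from DBS 1.2 "were 375 (316, 444), 774 (653, 917) and 1389 (1173, 1646) fmol/punch for 2, 4 and 7 doses per week respectively".

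**Accumulation from zero.** Fraction of plateau at day d = 1 − 2^(−d/h).
- Day 28: F/TDF 1 − 2^(−28/17) = 0.681 (0.750 to 0.570 over the half-life range); F/TAF 1 − 2^(−28/20) = 0.621 (0.660 to 0.603).
- Day 84: 0.967 and 0.946.

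**Day 28 medians and shares below the cut-off.** Day 28 value = observed-dosing value × fraction. Shares assume a log-normal with the documented median and sigma = ln(Q3/Q1)/(2 × 0.6745). Paired F/TAF figures are abstract / presentation.

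| Regimen | Cut-off | Median, observed dosing | Median, Day 28 | Share below cut-off, observed dosing → Day 28 |
|---|---|---|---|---|
| F/TDF daily (observed / fitted) | 700 | 1542 / 1389 | 1050 / 946 | 0.0% / 0.3% → 4.0% / 11.6% |
| F/TAF daily | 900 | 1928 / 2199 | 1197 / 1366 | 2.3% / 0.0% → 22.8% / 2.1% |
| F/TDF 67% (4.7 a week) | 700 | 946 | 644 | 14.0% → 61.8% |
| F/TDF 4 a week (fitted) | 700 | 774 | 527 | 34.5% → 87.1% |
| F/TAF 67% | 900 | 1351 / 1422 | 839 / 883 | 12.2% / 10.4% → 58.0% / 52.1% |
| F/TDF 2 a week (fitted) | 350 | 375 | 255 | 39.2% → 89.5% |
| F/TDF 33% (2.3 a week) | 350 | 518 | 353 | 12.4% → 49.1% |
| F/TAF 33% | 450 | 663 / 663 | 412 / 412 | 0.3% / 11.5% → 73.6% / 60.8% |

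For daily dosing the Day 28 lower quartile also stays High: 895 or 798 (F/TDF) and 948 or 1186 (F/TAF).

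**Early diagnosis.** The median daily user reaches cut-off c on day −h × log2(1 − c/median). For High this is Day 14.8 to 17.2 (F/TDF) and 15.2 to 18.1 (F/TAF). For leaving Low it is Day 6.3 to 7.1 and 6.6 to 7.7. At Day 14 full dosing reads 1542 × 0.435 = 671 (F/TDF) or 741 to 845 (F/TAF), all Medium. An equally adherent control at Day 28 reads 1050, or 1197 to 1366, all High.

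**Carry-over, the opposite error.** Assume plateau on daily F/TDF until Day 1 and no study drug afterwards. In the F/TDF arm, 1542 × 2^(−28/17) = 1542 × 0.319 = 492 at Day 28, which is Medium with no doses taken. In the F/TAF arm the SAP's larger punches have 10.89 times the area, so 1542 × 10.89 × 0.319 is about 5,400, against a High cut-off of 900.

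**The case against.** Several counter-arguments have weight.

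- **Daily users are not mislabelled at the scheduled visit.** A reader might infer that adherent participants in general are called Medium or Low at Week 4. The figures do not support that. The regimen is daily, the visit is at Day 28 ± 2 (Protocol Section 6.3), and daily users stay High at the median and lower quartile. Low needs sampling in about the first week. This stands.
- **The cohort plot bands nobody.** It shows group quartiles against reference lines. True; individuals are classified only in the case-control analysis.
- **Matching shares the error.** Cases and controls come from the same arm and window, and a control with several records contributes the one nearest the case's diagnosis day. At scheduled visits the misbanding is largely common to both. The nearest-record rule helps only when a control has more than one sample in the window. A differential error needs an unscheduled diagnosis. The protocol supplied collects DBS then (Section 6.6), but no count is given. A case sampled later than Day 28 would err the other way. A false adherence-infection link is therefore possible, not shown.
- **Early cases are partly handled.** DBS 1.4.7 has a sensitivity analysis setting adherence to Low where infection before first dose cannot be excluded. With no central antibody test scheduled on Day 1, most very early cases would fall there. It does not repair the main odds ratios, and it moves these cases in the same direction.
- **The bands may be protection thresholds.** The documents never call them steady-state, and the F/TDF bands come from a cohort linking concentration to HIV incidence. But Table 12 labels them in tablets a week, and that label fails at Day 28.
- **Timing.** SAP Section 8 says PK analysis was done and will not be repeated, although Section 4.2.3 still lists DBS analysis. Any change would be post hoc and should be labelled so.

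**Conclusion.** The point holds for the Week 4 window. With no prior F/TDF and first-order accumulation, 4 to 5 doses a week is mostly banded Medium instead of High: 52% to 87% fall below the High cut-off at Day 28, against 10% to 35% at observed-dosing levels. About 2 doses a week often becomes Low. Daily users mostly remain High at the scheduled visit. A daily user diagnosed before about Day 15 to 18 would read Medium, and in about the first week Low.

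The result assumes that the observed-dosing values are plateau values. The F/TAF shift rests on Week 12 data, and against Week 12 the Day 28 fractions are 70% and 66%, which changes nothing material. The F/TAF half-life is preliminary. Participants with baseline F/TDF can be over-called instead, most of all in the F/TAF arm; the documents give no share for them. The substudies lie outside the primary and alpha-controlled endpoints, so the main conclusions of the trial are not touched.

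**What to change.** Apply the adherence bands and threshold lines from Week 12 onward and report Week 4 as concentrations only. Add a sensitivity analysis of the case-control odds ratios that drops cases diagnosed in the Week 4 window together with their matched controls.

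Do not rescale the cut-offs for everyone. At Day 28 the F/TDF High cut-off would become 700 × 0.681 = 477, so a prior user at plateau on 33% dosing (median 518) would be called High, and over-calling from carry-over in the F/TAF arm would worsen. Any accumulation-scaled cut-off should be exploratory and limited to participants without baseline F/TDF.

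The cost is a few lines of SAP text and code on existing concentrations, and fewer cases in the sensitivity analysis. One limit remains: under the carry-over assumption above, the F/TAF-arm residue at Day 84 is 1542 × 10.89 × (1 − 0.967), about 550, still over the Low cut-off of 450. Week 12 bands in that arm should therefore be read with baseline F/TDF use in view.

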#### DBS 1.4. Case-Control Substudy

#### DBS 1.4.1. Study Design

Matched case control study nested in a clinical trial

## DBS 1.4.2. Objective

The primary objective of this case control evaluation is to assess the effect of adherence on HIV-1 PrEP efficacy (prevention of HIV-1 infection).

#### DBS 1.4.3. Definition of Case

All study participants who become HIV-1 infected after having been randomized to study treatment in the GS-US-412-2055 trial are the cases for this case-control substudy. The HIV-1 infection definition can be found in the SAP (Section 6.2.2).

#### DBS 1.4.4. Selection of Controls

A matching subset of the HIV-1 uninfected subjects will be selected as controls for this case-control substudy.

#### DBS 1.4.5. Matching

In this matched case-control substudy, control subjects will be matched to cases on a 5:1 ratio based on the following criterion order

- 1) Treatment group
- 2) Time of HIV-1 diagnosis, where time is defined as the visit that an HIV-1 case was first considered to be HIV-1 positive based on laboratory data; as subject visit varies, a visit window will be applied to identify the visit that is considered to be the HIV-1 infection visit. The visit windows for HIV-1 infection will be contiguous and centered at the mid-point of scheduled study visits (nominal day) as defined in Table 3-1 of the main SAP and the control subjects are selected based on the same visit windows as specified in Appendix Table 13.

## Appendix Table 13. Analysis Windows for Selection of Control Subjects

Visit ID	Nominal Day	Lower Limit	Upper Limit
Week 4	28	1	56
Week 12	84	57	126
Week K (K is every 12 weeks after Week 12 visit)	K*7	(K-6)*7+1	(K+6)*7

For both cases and controls, the concentrations from DBS at the time of HIV-1 diagnosis as well as at all previous post-baseline visits will also be measured to provide a clearer assessment of long term drug adherence.

- 3) Risk behavior as indexed by diagnosis of either rectal gonorrhea or rectal chlamydia (rectal STI [rSTI] collectively). Cases who are diagnosed with post-Day 1 rSTI prior to HIV-1 infection are matched to controls who are diagnosed with rSTI prior to HIV-1 infection time of the case subject (ie, a case subject who was diagnosed with HIV-1 at Week 48 and was diagnosed with rSTI prior to Week 48 is matched to control subjects who were diagnosed with rSTI between Day 1 and Week 48 in the study).
- 4) Location: As the number of subjects from each site varies, the matching location will be selected based on widening the geographic area in the following order to achieve the total number of controls
  - a) Investigational site (enrolled by the same investigator)
  - b) City (based on address)
  - c) Metropolitan area (based on address cities, grouping cities in close proximity such as Bronx and New York).
  - d) For US: i) State then ii) one of four US Regions (Northeast, Midwest, South or West as specified in Appendix 3.)

For Non-US: i) Country then Region; where European region includes UK and countries of Western Europe and for Canada, Region Country (Canada and the US are not pooled into one region due to differences in structure of social medicine).

Control subjects will be selected randomly if the available number of control subjects meeting the above criteria exceeds 5 in a site or a geographic area. For example, if there are 2 matching controls at the same investigational site and 10 additional in the same city (from other investigational sites), then the first two will be selected from the site and the next 3 will be picked randomly among the other 10 available in the same city.

Some subjects may move, due to personal reasons, from one city to another city, within a continent, while continuing in the study, the location criteria will be implemented based on the subject's current investigator and/or city (as tracked by the IxRS system).

Due to logistic issues at Covance (central warehousing lab for DBS cards), uninfected subjects who have intercontinental site transfers (North America ↔ Europe) during the study will not be selected as controls. As of September 2018, there were only 13 such subjects in the GS-US-412-2055 study.

A subject who meets the above criteria but is diagnosed with HIV-1 at a later date compared to the case subject (later than the upper limit of the window) is allowed to be selected as a control subject (ie, a subject who is HIV-1 infected at Week 60 may serve as a control for a Week 12 infection if other matching criteria are met).

#### DBS 1.4.6. Implementation

In order to lower the burden on the laboratory analyzing DBS cards, selection of matches may be done in batches as subjects complete study visits (upper bound of visit window as specified above). Control subjects, who have available DBS cards, will be identified from the pool of HIV-1 negative subjects matching to each case subject. For example, when all subjects complete the Week 24 visit (plus 6 weeks) then the matching controls could be selected for all infections on or prior to Week 24. A SAS program will be utilized for the random selection of controls based on DBS accession numbers. A uniform random number will be assigned to each DBS accession number. The rank of the random numbers will be used for random selection of controls. Thus, the samples from the first 5 ranked subjects will be selected.

A date stamped dataset for each infected subject (case) with all the details on available control subjects will be generated and archived for future reference.

As the first matching criterion is treatment group, the unblinded statistician supporting the external DMC will execute the SAS program to:

- 1) Provide the accession number of the selected DBS cards to Covance (central warehousing lab for DBS cards) for transfer to the analytic lab (University of Colorado). Covance will receive the following information: Investigator ID, Subject ID, Lab Date, Accession Number, and Container Number (of sample storage at Covance).
- 2) Provide the treatment code for each accession number to the analytic lab as measuring DBS concentration for F/TAF requires a bigger punch-hole on the DBS card compared to F/TDF. The analytic lab will receive the following information: Investigator ID, Subject ID, Lab Date, Treatment group and Accession Number.

The DBS concentration data for each batch will be transferred to the unblinded statistician. The unblinded statistician will manage the data batches to create datasets for DBS concentrations and identify HIV infected subjects (cases) and their matched controls, including Subject ID, investigator ID, treatment group, strata ID (to indicate a case and matched controls), sample date,

sample day (relative to Day 1), concentration and other relevant data. This dataset will be transferred to Gilead after study unblinding for the primary analysis. The raw Excel files (and their PDF versions) for each batch will be sent to Gilead from both the unblinded statistician and the analytical lab (University of Colorado) for long term archiving.

This process protects the integrity of the study as it insures that the staffs at Gilead and Covance remain blinded to the study drug assignment at the subject level.

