### Appendix 1. Study Procedures Table

### **Appendix Table 1. Study Procedures Table**

	Screening	Day 1			Dou		Blind ' d of W		ment			Post Week 96	Open Label Treatment End of Week c									
Study Procedure			4	12	24	36	48	60	72	84	96	Every 12 Weeks	End of Blinded Treatment Phase Visit b	12	24	36	48	Every 12 Weeks d	30 Day Follow up e	ESDD f		
Informed Consent	X																					
Medical History	X																					
Concomitant Medications	X	X	X	X	X	X	X	X	X	X	X	X	X	X	X	X	X	X	X	X		
Adverse Events		X	X	X	X	X	X	X	X	X	X	X	X	X	X	X	X	X	X	X		
Complete Physical Exam	X						X				X						X					
Targeted Physical Exam		Xº	X	X	X	X		X	X	X		X	X	X	X	X		X	X	X		
Vital Signs g	X	Xº	X	X	X	X	X	X	X	X	X	X	X	X	X	X	X	X	X	X		
Weight	X	X	X	X	X	X	X	X	X	X	X	X	X	X	X	X	X	X	X	X		
Height	X																					
Genital, Rectal, and Pharyngeal Examination for STIs as appropriate	X		X	Х	X	X	Х	Х	Х	Х	Х	X	Х	Х	Х	X	Х	X	Х	X		
Pharyngeal Swab for Gonorrhea and Chlamydia ac (Local Laboratory)	Х		Х	Х	Х	X	X	X	X	Х	Х	х	Х	Х	Х	Х	Х	Х	Х	X		
Rectal Swab for Gonorrhea and Chlamydia (Local Laboratory) ac	X			х	X	X	Х	Х	X	х	х	Х	X	х	х	X	Х	X	X	X		
Urine Sample for Gonorrhea and Chlamydia	X		X	Х	X	X	X	X	X	Х	Х	X	X	Х	Х	X	X	X	X	X		
Rapid HIV 1 Ag/Ab Test (In Clinic) p	X	X	X	X	X	Х	X	X	Х	X	X	X	X	X	X	X	X	X	X	X		
HIV 1 Ab/Ag q	X		X	X	X	X	X	X	X	X	X	X	X	X	X	X	X	X	X	X		

	Screening				Dou		Blind d of V	Treati Veek a	ment			Post Week 96	Open Label Treatment End of Week c								
Study Procedure		Day 1	4	12	24	36	48	60	72	84	96	Every 12 Weeks	End of Blinded Treatment Phase Visit b	12	24	36	48	Every 12 Weeks d	30 Day Follow up e	ESDD f	
HIV 1 RNA by PCR r	X	Xs	X	X	X	X	X	X	X	X	X	X	X	X	X	X	X	X	X	X	
Dipstick Urinalysis (In Clinic)	X																				
Urinalysis, Urine Protein, Urine Chemistry	X		X	X	X	X	X	X	X	X	X	X	X	X	X	X	X	X	X	X	
CCI																					
Blood Sample for Chemistry Profile h	X		X	X	X	X	X	X	X	X	X	X	X	X	X	X	X	X	X	X	
Blood Sample for Hematology Profile i	X		X	X	X	X	X	X	X	X	X	X	X	X	X	X	X	X	X	X	
Blood sample for DBS j			X	X	X	X	X	X	X	X	X	X	X	X	X	X	X	X			
Blood Sample for Syphilis testing k (Local Laboratory)	X		X	Х	X	Х	X	Х	Х	X	X	X	X	Х	X	X	X	X	Х	X	
Hepatitis B Testing (HBsAg/HBsAb/HBcAb)	X				X		X		X		X	X ad	X ad		X		X	X ad			

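### DBS case-control substudy: a card is required of controls but imputed for cases, so some people tested for HIV without a card can enter only as cases

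*SAP*

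**What the plan says.** **Controls.** DBS 1.4.6 states: "Control subjects, who have available DBS cards, will be identified from the pool of HIV-1 negative subjects matching to each case subject". The random draw runs on card accession numbers. DBS 1.4.7 takes the control's value from a card inside the case's visit window; its tie rule begins "If a control subject has DBS collected at more than one visit within a window". The need for a card in that window is implied, not stated as a rule.

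**Cases.** DBS 1.4.3 defines them as "All study participants who become HIV-1 infected after having been randomized to study treatment", with no card condition. SAP 6.2.2 lets a local test done outside the study set the diagnosis date.

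**Missing values.** DBS 1.4.7 expects gaps among cases: "DBS cards at the time of diagnosis may not have been collected for infected subjects or the sample may not meet specifications". It continues: "In general, missing DBS concentration at the time of HIV diagnosis will be imputed by considering" the last earlier concentration, days since last dose (negative values set to zero), days since the last DBS and a half-life decay rate. SAP 3.6.1 also ties the rule to HIV diagnosis. No counterpart is given for controls. The only sensitivity analysis listed for the odds ratios sets suspected pre-dose infections to Low adherence.

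**Schedule.** In SAP Appendix Table 1 the row "Blood sample for DBS" is marked at every scheduled visit from Week 4 and blank at the 30-Day Follow-up and early study drug discontinuation (ESDD) visits. HIV testing is marked at both. SAP 6.2.3 counts time at risk up to the last HIV test, which may be the 30-day visit. Protocol 6.6 requires DBS at an unscheduled visit only for those who test HIV positive.

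**The concern.** Controls in a nested case-control study should show the exposure of the people who were at risk when the case occurred. Here, having an exposure measurement is an entry condition on one side only.

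Take two participants who stop drug, leave the study and attend the 30-day visit. The one found infected is a case, valued by decay from the last dose. The uninfected one has two possible outcomes:

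- The last card lies in an earlier window. That person cannot be a control for this window.
- The last card lies in the same window, which is 84 days wide from Week 24. That person is eligible, but with a value from before drug was stopped and no decay applied.

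The same can happen with outside tests and missed scheduled visits. Either way, controls may look more adherent than the people at risk. The substudy exists to assess how adherence relates to protection (DBS 1.4.2), and the planned example has only 10 cases per arm (DBS 1.5), so one or two such cases could matter.

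**Working it through.** The plan gives no figure for this effect. From DBS 1.5 I take the design of 10 cases with 5 controls each, 10 × (1 + 5) = 60 subjects per arm, and the odds ratio of 0.10. Nothing below uses the stated power.

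**Step 1: does decay change the adherence category?**

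Inputs:
- Half-lives of 17 days (F/TDF) and 20 days (F/TAF), from DBS 1.4.7.
- Medians under daily dosing from Appendix Table 11: F/TDF 1542; F/TAF 2199 (presentation) or 1928 (abstract).
- Cutoffs from Appendix Table 12: High from 700 and Low below 350 (F/TDF); High from 900 and Low below 450 (F/TAF).
- A 30-day visit falling 30 to 44 days after last dose (Protocol 6.7.3).

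Assumed form, since the SAP's own equation is not visible: C(t) = C0 × exp(−k·t), with k = 0.693 / half-life.

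| | Day 30 | Day 44 | Below High | Into Low |
|---|---|---|---|---|
| F/TDF, 1542 | 454 (Medium) | 257 (Low) | day 19 | day 36 |
| F/TAF, 2199 | 778 (Medium) | 479 (Medium) | day 26 | day 46 |
| F/TAF, 1928 | 682 (Medium) | 420 (Low) | day 22 | day 42 |

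A former daily doser found infected at day 30 is therefore imputed Medium in either arm. At an ESDD visit 3 days after the last dose, F/TDF would be 1542 × exp(−0.693 × 3/17) ≈ 1364, still High. The 30-day visit matters; the missing ESDD card does not in itself point to low exposure.

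**Step 2: high versus not high, assumed true odds ratio 0.10.** Let P be the true share of High among eligible controls and f the share left out for lack of a card, all assumed not High. Then

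OR observed = 0.10 × (1 − P − f) / (1 − P).

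| P | f = 1% | f = 2% | f = 5% |
|---|---|---|---|
| 0.5 | 0.098 | 0.096 | 0.090 |
| 0.8 | 0.095 | 0.090 | 0.075 |
| 0.9 | 0.090 | 0.080 | 0.050 |

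If instead a share g of controls is wrongly classed High on a pre-stop card, the controls' High odds rise from P/(1 − P) to (P + g)/(1 − P − g). With P = 0.8 and g = 2%, the odds go from 4 to 0.82/0.18 = 4.56, and the odds ratio from 0.10 to 0.088. Both routes push the same way.

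**Step 3: low versus not low, assumed true odds ratio 10.** Let L be the share of Low among eligible controls.
- If those left out are all Low: OR = 10 × L / (L − f). With L = 10% and f = 2%, 12.5, away from 1.
- If those left out are Medium, as at day 30: OR = 10 × (1 − L − f) / (1 − L). With the same inputs, 10 × 0.88/0.90 = 9.8, toward 1.

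The direction depends on who is left out.

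**Step 4: what values of f are plausible?** If those without a card are people leaving the study, each is lost mainly in the final window. Over eight 12-week windows, a share f per window implies cumulative exit of 1 − (1 − f)^8: 15% for f = 2%, 34% for 5%, 57% for 10%. Large shares are hard to reach by this route alone.

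**The case against.** A reader might infer that anyone who stopped drug can become a case but never a control. The documents do not support that. Participants may stay in the study off drug (SAP 1.2, Protocol 3.2), scheduled evaluations continue whether or not drug is taken (Protocol 6.3), and SAP 1.2 has DBS taken from Week 4 at all later visits. Only the plasma PK sample is written to end at drug discontinuation. Off-drug attenders have DBS scheduled and can be controls.

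Other points on that side also stand:
- Leaving people out of windows after their last HIV test is correct, because they add no further time at risk.
- Cases who test positive at an unscheduled visit have a card taken, and a case still on drug has days since last dose set to zero. Imputation with decay is not universal.
- The rule on freezing cards within a day (DBS 1.1) applies to both groups and gives no reason to expect low adherence among the cards lost.
- Bias away from 1 is not general: step 3 shows the low-versus-not-low odds ratio can move toward 1.
- The substudy is supportive. SAP Section 8 says the PK analysis was done at the primary analysis and is not repeated, and DBS 1.4.6 has the dataset transferred after that unblinding.

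These points narrow the group and the claim. They do not remove the differing entry rules, and no planned analysis tests their effect.

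**Conclusion.** The asymmetry holds: card availability selects controls, while cases without a card are kept and imputed. It affects participants whose HIV test in the matched window had no card, mainly at the 30-day visit, in outside tests or around missed visits. They can enter as cases but not as controls, or as controls on an undecayed pre-stop card.

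The high-versus-not-high odds ratio would tend to be pushed away from 1. For low versus not low, the direction is uncertain. The size cannot be determined from the documents: f, g, P and L are assumptions, as are the exponential form and the premise that those left out were not High. Shares of 1% to 2% shift the illustrative 0.10 to between 0.080 and 0.098, and the effect may be small. Two limits apply: the Protocol's DBS entries are partly redacted, and the SAP's imputation equation is not visible.

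**What to change.** Make three additions to DBS 1.4.7:

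1. A sensitivity analysis of both odds ratios restricted to matched sets in which the case has a measured, non-imputed card at diagnosis.
2. One decay rule for both groups. Where a control's selected card precedes that control's last dose date or the case's diagnosis day, apply the last-dose rule used for cases, with no decay while still on drug.
3. A count of otherwise matched HIV-negative participants left out for lack of a card, by on-drug or off-drug status and treatment group.

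If the substudy has already been analysed, these can be supplementary analyses of existing data. The cost is SAP text and programming; no new blood is drawn. The downside is precision: each restricted-out case removes 6 of the planned 60 subjects in its arm, so intervals widen.

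Re-drawing controls regardless of card availability is optional. It would come closer to sampling everyone at risk, but imputing the newly chosen controls would require more stored cards to be shipped and assayed.
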